12.2 Sample Size Determination

A group size of 28 completers was selected for use in this study based on an assumed effect size of 0.7 suggested by similar alcohol self-administration studies with amount consumed as the primary outcome^{42,44}. This effect size is in the range we found for the anticonvulsant zonisamide used in a similar alcohol self-administration study⁴³. The sample size for this study is based on an estimated reduction of 1.5 standard drinks with an estimated standard deviation (2.1) of the between Challenge Trial differences in alcohol self-administration, with an effect size

The Effects of Exenatide, a GLP-1 Agonist, on Alcohol Self-Administration in Heavy Drinkers
Version 1.8 10.5.20

of this magnitude (i.e. 0.7). This requires a sample size of 28 to allow for detection of a significant within-subject difference in alcohol consumption with an alpha value of 0.01 and power value of 0.81. Based on an estimated 15-20% rate of non-completion for randomized subjects, we anticipate randomizing 36 subjects to achieve a sample of 28 completers. Given our experience with recruiting AUD populations into clinical trials, we expect a screening exclusion rate of roughly 50%. Approximately 72 subjects will be consented and screened in clinic to yield a sample of 36 eligible subjects.

Given that this a laboratory based experiment we do not plan to conduct any planned interim analyses in this study.

13 Ethics/Protection of Human Subjects

This study is to be conducted according to applicable US federal regulations and institutional policies (which are based in federal regulations, guidance, and ICH Good Clinical Practice guidelines).

This protocol and any amendments will be submitted to the Boston Medical Center and Boston University Medical Campus IRB, for formal approval of the study conduct. The decision of the IRB concerning the conduct of the study will be made in writing to the investigator. A copy of the initial IRB approval letter will be provided to the sponsor before commencement of this study.

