12.1 Study Hypotheses and Planned Analyses

For our primary outcomes, data from subjects who experience moderate to severe nausea during the alcohol self-administration trials will be excluded from our statistical analysis. Although the dosing chosen for this study minimizes the potential for nausea as a medication side effect, this may occur in some subjects. These subjects will be excluded from analyses as medication-induced nausea could confound the drinking outcomes. The presence of nausea will be established by a rating greater than 30 on a VAS scale that rates nausea from no nausea to unbearable nausea⁵³.

Hypothesis	Proposed Analyses
1. Subjects will consume less alcohol during an alcohol Challenge Trial when receiving exenatide	The volume of alcohol consumed during alcohol challenge trials 1 and 2 will be used to test the effect of exenatide on alcohol consumption. We will use a mixed

The Effects of Exenatide, a GLP-1 Agonist, on Alcohol Self-Administration in Heavy Drinkers
 Version 1.8 10.5.20

compared to when they receive a sham injection.	models repeated measures approach to test for differences between alcohol consumption between the exenatide and sham injection self-administration trials ⁵⁴⁻⁵⁵ . This data will be divided into first and second-hour blocks of self-administration. Within-subject factors for this analysis will include Treatment and Time Block. Trial order will be used as covariate in these analyses to allow evaluation as to whether the order of treatments had a significant effect on the outcome. Appropriate covariance structures will be determined using Akaike's information criteria to evaluate the best model fit. Results analysis will be examined for both treatment effects and the Treatment x Time Block interaction results.

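### Does the power of 0.81 in section 12.2 fail because section 12.1 also removes subjects with nausea?

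*Combined protocol and SAP*

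**What the plan says.** Section 12.2 sets the target: "A group size of 28 completers was selected for use in this study based on an assumed effect size of 0.7". The effect size is backed by an assumed reduction of 1.5 standard drinks and an SD of 2.1 for the within-subject differences, with alpha 0.01 and power 0.81. The step up to 36 randomised is put as "we anticipate randomizing 36 subjects to achieve a sample of 28 completers" and is explained by one loss after randomisation: "Based on an estimated 15-20% rate of non-completion for randomized subjects". The only other loss in 12.2 is screening exclusion of about half, which comes before randomisation.

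Section 12.1 states a further loss, for the primary outcomes: "data from subjects who experience moderate to severe nausea during the alcohol self-administration trials will be excluded from our statistical analysis". The cut-off is a nausea VAS rating above 30. On frequency, 12.1 says only this: "Although the dosing chosen for this study minimizes the potential for nausea as a medication side effect, this may occur in some subjects". Section 12.2 does not mention the exclusion, and no replacement rule is written.

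**The concern.** Power belongs to the number of subjects analysed, and 12.2 attaches it to the number who complete. The two can differ. Section 9 has nausea rated at the end of the session, and Appendix B lists it at the end of each drinking block. A subject who rates above 30 in Trial 2 has therefore normally finished both trials. That subject counts as a completer and is then removed, which the 15-20% allowance does not obviously cover.

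If such removals were common, the primary comparison would rest on fewer than 28 pairs and its power would be below the stated 0.81. After a null result, a reader of 12.2 alone would credit the trial with more sensitivity than it had.

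**Working it through.** **Inputs.** From 12.2: alpha 0.01, power 0.81, effect size d = 0.70 (or 1.5/2.1 = 0.714 from the stated reduction and SD), 28 completers, 15-20% non-completion, 36 randomised. From 12.1: exclusion at nausea VAS above 30, with no rate. Section 12.2 does not state sidedness; two-sided is assumed because it reproduces the plan's figure.

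**Step 1: reproduce 0.81.** For a paired t-test, power = P(|T| > t[0.995, n-1]), where T is noncentral t with n-1 degrees of freedom and noncentrality d√n.

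- d = 0.70, n = 28: noncentrality 0.70 × √28 = 3.70, power 0.815.
- d = 0.714, n = 28: noncentrality 0.714 × √28 = 3.78, power 0.834.
- Using n-2 degrees of freedom, for a period term, gives 0.813 and 0.831.
- A one-sided t-test at d = 0.70 would give 0.883, and a two-sided normal approximation 0.870.

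The stated 0.81 is therefore the two-sided paired t-test at d = 0.70 with 28 analysed pairs.

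**Step 2: check the step from 28 to 36.** 28/0.85 = 32.9, so 33 randomised; 28/0.80 = 35. The plan takes 36. Expected completers are 36 × 0.80 = 28.8 to 36 × 0.85 = 30.6, that is, 0.8 to 2.6 above target. Total loss could reach 1 - 28/36 = 22.2% before fewer than 28 remain.

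**Step 3: power by number analysed** (two-sided alpha 0.01).

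| Analysed | d = 0.70 | d = 0.714 |
|---|---|---|
| 30 | 0.850 | 0.866 |
| 29 | 0.833 | 0.851 |
| 28 | 0.815 | 0.834 |
| 27 | 0.796 | 0.815 |
| 26 | 0.775 | 0.794 |
| 25 | 0.752 | 0.772 |
| 24 | 0.727 | 0.748 |

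The loss is about 2 points per subject. With the plan's own 1.5/2.1, 27 analysed subjects still give 0.815.

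**Step 4: how much exclusion the margin absorbs.** Power reaches 0.81 at n = 27.716 (d = 0.70) or 26.753 (d = 0.714), interpolating between whole subjects. Treating nausea exclusion as additional to non-completion:

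- d = 0.70: 1 - 27.716/28.8 = 3.8% to 1 - 27.716/30.6 = 9.4%.
- d = 0.714: 1 - 26.753/28.8 = 7.1% to 1 - 26.753/30.6 = 12.6%.

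These limits use power at the expected number analysed. Averaging power over a binomial number analysed lowers them to 2.9-8.6% and 6.1-11.6%. Taken together, the range is roughly 3-13%.

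**Step 5: illustrations under assumed rates.** Expected number analysed = 36 × (1 - non-completion) × (1 - exclusion). Power is taken at that number, for 20% and then 15% non-completion.

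| Assumed exclusion | Expected analysed | d = 0.70 | d = 0.714 |
|---|---|---|---|
| 0% | 28.8; 30.6 | 0.830; 0.859 | 0.847; 0.875 |
| 5% | 27.4; 29.1 | 0.803; 0.835 | 0.822; 0.852 |
| 10% | 25.9; 27.5 | 0.773; 0.807 | 0.793; 0.825 |
| 20% | 23.0; 24.5 | 0.702; 0.739 | 0.723; 0.760 |

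Independence of the two losses is the pessimistic case, since a subject nauseated in Trial 1 who does not return is already a non-completer. If half of a 10% exclusion overlaps in this way, the 5% row applies.

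**The case for a change.** The case for acting is that the plan pre-specifies both an exclusion and a power and never connects them. The slack in 36 is small and 12.2 credits it to non-completion alone, so a reader cannot tell whether it was meant to cover nausea as well. Section 12.1 itself expects some exclusions, and its wording reaches nausea in either trial, whatever the cause. At an assumed 20% exclusion, power would be 0.70-0.76, which is not trivial. Two sentences would settle the matter.

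The omission is real, and the distinction between completing and being analysed is correct. The step from there to a shortfall is not supported. Section 6.1 reports nausea incidences from 0% to 65%, but at other doses, in other populations and by other definitions. None is a rate of VAS above 30 after a single 5 mcg dose with alcohol, so any percentage put into 12.2 would be a guess. The documents also do not define a completer or say that nausea losses lie outside the 15-20%. And 36 is an anticipated number, with about 72 to be screened and, under section 5, recruiting services available until recruitment goals are met. An added sentence would record an assumption and leave the trial as it is.

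**Conclusion.** The concern does not call for a change. The 0.81 is correct for 28 analysed pairs, the step to 36 is correct for 15-20% non-completion, and it leaves a small margin that absorbs roughly 3-13% nausea exclusion among completers. Beyond that, the cost is about 2 points of power per subject below 28. The documents do not show that exclusions will exceed the margin; equally, they do not show that they will stay within it.

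This rests on a two-sided test, on nausea losses being additional to non-completion, on whole subjects being removed, and on the effect and SD being the same in those who remain. It also uses a paired t-test as a stand-in for the planned mixed model. Whether excluding subjects on a rating made after treatment is a sound choice of analysis is a different question from this count.

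What remains is a gap in documentation that analysts fill in the ordinary way: they read 0.81 as applying to 28 analysed subjects and report the number excluded for nausea, with the confidence interval for the number actually analysed. That interval tells the reader of a null result more than an assumed rate in 12.2 would.

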	Baseline (May be split over 2 visits)	Randomization & Trial1	Trial 2
Clinic Visit #	0	1	2
COVID-19 Screening Questionnaire (pre-visit)	X	X	X
Informed Consent	X		
Urine Drug Screen ^A	X	X	X
Locator Form	X		
Demographics	X		
Medical History	X		
Physical Exam	X		
MINI V 6.0	X		
CBC w Diff AST, ALT, GGT, Tbili, BUN, Ca, CO2, Cl, Cr, G K, Na, Triglycerides, Serum lipase, Ha1c	X		
Vital Signs, weight, Blood Alcohol Level ^{b, c}	X	X	X
ECG	X		
Prior and Concomitant Meds	X	X	X
CIWA-AR	X	X	X
Eligibility Checklist		X	
Confirm Eligibility to continue		X	X
Urine Pregnancy Test	X	X	X
Birth control assessment	X	X	X
AEs	X	X	X
C-SSRS	X	X	X
Treatment Referral			X
TLFB (28 day at baseline)	X	X	X
Alcohol Craving VAS ^c		X	X
OCDS ^c	X	X	X
AUQ ^c		X	X
Nausea VAS		X	X

The Effects of Exenatide, a GLP-1 Agonist, on Alcohol Self-Administration in Heavy Drinkers
Version 1.8 10.5.20

	Baseline (May be split over 2 visits)	Randomization & Trial1	Trial 2
Clinic Visit #	0	1	2
Blood Glucose (at end of block2)		X	X

A) Test for opioids, cocaine, amphetamines, methamphetamine, tetrahydrocannabinol (THC), barbiturates, oxycodone, buprenorphine, methadone and benzodiazepines, and alcohol (Ethyl Glucuronide)
B) if the baseline visit is split between two days, vitals, breathalyzer, and weight are to be taken at each visit.
c) See Table 2 for specific administration times

Items highlighted in blue will be performed in-clinic remote. The study staff and subject will connect through video call while located in separate rooms in the Clinical Studies Unit to avoid unnecessary face-to-face contact. Forms that must be filled out by the subject will be left on a clipboard in the exam room to be occupied by the subject, and study staff will instruct subjects to fill out the forms. Forms filled out by study staff through interviewing the subject will be kept in the study staff's room. The COVID-19 screening questionnaire will be administered before the subject arrives for their in-clinic visit.

Items highlighted in yellow will be performed with social distancing. The study staff and subject will be located in the same room, but will maintain a 6-foot distance and both persons will wear PPE at all times.

Items highlighted in green require direct contact between study staff and subject. Contact will be limited to minimum necessary and PPE will be worn at all times by both study staff and subject.

The Effects of Exenatide, a GLP-1 Agonist, on Alcohol Self-Administration in Heavy Drinkers
Version 1.8 10.5.20

16. Appendix B: Schedule of assessments during drinking lab

	Pre-challenge	Observation	Self-admin Block1	Self-admin Block2
Assessment				
BAC	Prior to drug admin	Every 10 minutes	Every 30 minutes	Every 30 minutes
VAS-Alcohol Craving	Prior to drug admin	Every 10 minutes	Every 30 minutes	Every 30 minutes
AUQ	Prior to drug admin	At end of observation	Every 30 minutes	Every 30 minutes
OCDS	Prior to drug admin	None	None	None
VAS-Nausea			End of block	End of block
